[figure not shown]

Impact Of Post-Bariatric Body Contouring Procedures on Patient Body Weight and Metabolism

NCT05034081

Date of document 2\3\2026

[School]
[Course title]

Patients and methods

This is a prospective comparative study on 60 patients will be conducted on post-bariatric patients seeking for body contouring surgery from 2021 to 2025.

The primary contouring procedures will be analyzed including panniculectomy, abdominoplasty, and lower body lift. Brachioplasty, mastopexy with breast reduction or augmentation, arm and thigh lift, liposuction, facelift, and pubic/genital plasty procedures were identified and considered as “other procedures.”

Weight of the resected tissue will be recorded. Patient demographic characteristics included age, gender, and body mass index (BMI) both before and at the last available follow-up visit after bariatric surgery. Thorough patient co-morbidity assessments were performed. This cohort of patients was then matched and compared with a 1:1 control group of patients who had only undergo for bariatric surgery. Matching will be based on age, gender, BMI at the time of bariatric surgery, type of bariatric surgery procedure, and length of follow-up.

These patients will be divided into 2 groups. Group (A): 30 patients will do Post-bariatric body contouring procedure . Group (B): 30 patients as a control group will not do body contouring surgery.

Body Contouring Surgery will performed when the patient's weight has been stable within 5 kg for at least 3 months.

The Patients will have a fixed diet plan through the time of the study and diet will be given according to BMR

Men: $BMR = 88.362 + (13.397 \times \text{weight in kg}) + (4.799 \times \text{height in cm}) - (5.677 \times \text{age in years})$

Women: $BMR = 447.593 + (9.247 \times \text{weight in kg}) + (3.098 \times \text{height in cm}) - (4.330 \times \text{age in years})$

Weight and BMI documentation will occur after body contouring surgery before body contouring surgery and 3 and 6 months after.

Routine investigations (CBC, UR & CR, Lipid profile and RBS) will be done before body contouring surgery and 6 months after.

Measurement of post-bariatric body metabolism will be done by measurement of $TNF-\alpha$, hsCRP and BNP before body contouring surgery and 3 and 6 months after.

Patient satisfaction score from 1 to 5 done 2 months post body contouring surgery. The weight of excised skin and fat in contouring surgery will be documented and removed from the net weight loss.

Inclusion criteria:

- Post-bariatric (sleeve) patients will do body contouring surgery.
- Post-bariatric patients has been stable within 5 kg for 3 months
- Age between 20-60 years old.
- patients use the determinant fixed diet.

Exclusion criteria:

- Age below 20 and above 60 years old.
- Non-compliance with the fixed diet.
- psychotic patients.
- Female patients seeking pregnancy.
- Endocrine causes of obesity.
- Bariatric surgery other than sleeve.

Procedures data:

- Demographic data
- Type of bariatric surgery
- Type of plastic operation
- Age of patient
- Timing of applying the methodology

Post-procedure data

- Weight changes
- Patients satisfaction score
- patient metabolism by hsCRP, TNF- α and BNP.

Evaluation of the patients:

1- patient weight and BMI:

Documentation of the patient weight and BMI after post-bariatric body contouring surgery for 6 months.

2- patient satisfaction score:

patient satisfaction score from 1 to 5 done 2 months post body contouring surgery.

Question	Score
How satisfied are you with the results of your surgery?	
Very satisfied	5
Somewhat satisfied	4
Neither satisfied nor dissatisfied	3
Somewhat dissatisfied	2
Very dissatisfied	1

3- Type of patient metabolism:

Detect patient metabolism by doing TNF- α , hsCRP and BNP before the body contouring surgery and 3 and 6 months after. Routine investigations (CBC, UR & CR, Lipid profile and RBS) will be done before body contouring surgery and 6 months after.

Statistical analysis

Statistical analysis was done by SPSS v26 (IBM Inc., Chicago, IL, USA). Quantitative variables were presented as mean and standard deviation (SD) and compared between the two groups utilizing unpaired Student's t- test. Qualitative variables were presented as frequency (%) and were analyzed utilizing the Chi-square test or Fisher's exact test when appropriate. A two tailed P value ≤ 0.05 was considered statistically significant.

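### Co-morbidity is assessed but neither matched on nor adjusted for, so a co-morbidity difference between operated patients and controls could be reported as an effect of contouring

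*Combined protocol and SAP*

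**What the plan says.** The Patients and methods section describes a prospective comparison of 60 post-bariatric patients: "Group (A): 30 patients will do Post-bariatric body contouring procedure" and "Group (B): 30 patients as a control group will not do body contouring surgery". No random allocation is described. Among the patient characteristics it states that "Thorough patient co-morbidity assessments were performed". It gives no list of conditions, no scale and no use for the result.

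The contouring cohort is then "matched and compared with a 1:1 control group of patients who had only undergo for bariatric surgery". The matching factors are stated in full: "Matching will be based on age, gender, BMI at the time of bariatric surgery, type of bariatric surgery procedure, and length of follow-up". Co-morbidity is not among them.

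In the Statistical analysis section, quantitative variables are "compared between the two groups utilizing unpaired Student's t- test". For the rest, "Qualitative variables were presented as frequency (%) and were analyzed utilizing the Chi-square test or Fisher's exact test when appropriate". No covariate, stratification, propensity method or sensitivity analysis is mentioned.

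The only disease-related exclusions are psychosis and endocrine causes of obesity. Co-morbidity does not appear in the Procedures data list.

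**The concern.** Group membership depends on who has elective surgery. Fitness for surgery is a natural reason for operated patients and controls to differ in co-morbidity. TNF-alpha, hsCRP and BNP are inflammatory and cardiac markers, which chronic disease and its treatment can plausibly shift. A factor linked to both group and outcome confounds an unadjusted comparison, and the plan has no step that would remove the effect of such a difference if it existed.

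The one use the plan could make of the co-morbidity data is a chi-square or Fisher comparison of the groups. That can describe an imbalance but cannot correct for it, and at 30 per group it often fails to flag one.

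Adjusting for the outcome's baseline value would help but would not be sufficient. Co-morbidity and its treatment can also affect how weight and the markers change over the following 6 months. At stake is the study's central inference, which is the comparison with controls.

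**Working it through.** The plan states no effect size, SD or sample-size derivation, so there is no figure of its own to reproduce. The check is an illustration.

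**From the documents:** n = 30 per group; unpaired t-test; two-sided significance at P ≤ 0.05.

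**Assumed, because the documents give nothing:** a binary co-morbidity with prevalence pA in Group A and pB in Group B; an outcome shift of g SD in those who have it; residual SD 1; no true effect of contouring.

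**Step 1, bias.** Spurious difference = (pA − pB) × g. Smallest case: (0.20 − 0.40) × 0.2 = −0.04 SD. Largest case: (0.15 − 0.45) × 1.0 = −0.30 SD.

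**Step 2, false-positive rate.** SE = √{[2 + g²(pA(1 − pA) + pB(1 − pB))]/30} and δ = |bias|/SE. The rejection rate is about Φ(−1.96 + δ) + Φ(−1.96 − δ).

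- 20% v 40%, g = 1.0: SE = √[(2 + 0.16 + 0.24)/30] = 0.283; δ = 0.20/0.283 = 0.707; rate = Φ(−1.253) + Φ(−2.667) = 0.109.
- 15% v 45%, g = 1.0: SE = √[(2 + 0.1275 + 0.2475)/30] = 0.281; δ = 0.30/0.281 = 1.066; rate = 0.187.

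| g (SD) | Bias, 20% v 40% | Rate | Bias, 15% v 45% | Rate |
|---|---|---|---|---|
| 0.2 | −0.04 | 5.3% | −0.06 | 5.6% |
| 0.3 | −0.06 | 5.6% | −0.09 | 6.4% |
| 0.5 | −0.10 | 6.7% | −0.15 | 8.8% |
| 0.8 | −0.16 | 9.0% | −0.24 | 14.2% |
| 1.0 | −0.20 | 10.9% | −0.30 | 18.7% |

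Simulation of the t-test itself agrees with these rates to within about one percentage point.

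**Step 3, adjustment for the true confounder.** Adding the causal co-morbidity to a linear model brings the simulated bias to about 0 and the false-positive rate to 4.8% to 5.1%.

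**Step 4, adjustment for a coarser summary.** Suppose there are three conditions: one causal (20% v 40%, 0.8 SD) and two irrelevant (30% in both groups). Over 20,000 simulated trials:

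| Covariate | Remaining bias (SD) | Share removed | False-positive rate |
|---|---|---|---|
| None | −0.16 | – | 8.7% |
| Any v none | −0.127 | about 21% | 7.2% |
| Count | −0.110 | about 32% | 6.7% |
| Causal condition | 0.00 | all | 4.9% |

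**Step 5, whether a baseline test would reveal the imbalance.** Exact power at 30 per group:

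| Imbalance | Chi-square | Fisher's exact |
|---|---|---|
| 20% v 40% | 39% | 30% |
| 15% v 45% | 74% | 64% |

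A non-significant result is weak evidence of balance.

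**The case against.** The strongest reply is that the harm is hypothetical. The documents show no imbalance and no effect of co-morbidity on any outcome. Several features narrow the scope for one:

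- matching on age, gender and BMI at bariatric surgery balances co-morbidity as far as it follows those factors;
- eligibility is limited to sleeve patients aged 20 to 60 with stable weight;
- all patients are on a fixed diet.

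The plan also speaks of weight changes, and of taking the excised tissue out of net weight loss. If change is what is analysed, a stable difference in level cancels for weight. What is left is the effect of co-morbidity on 6-month change, which may be small: at 0.2 to 0.3 SD with 20% v 40%, the false-positive rate is only about 5.3% to 5.6%.

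Much of this stands. It rules out saying that nothing in the design balances co-morbidity, and it is why the range starts at 0.2 SD. It does not close the gap. Matching on four factors that can vary (procedure type cannot, as only sleeve is eligible) leaves any co-morbidity difference unrelated to them. The plan does not say whether changes or follow-up values of the markers enter the t-test. Change scores also do not remove an effect on the course after baseline.

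A reader might also infer that every patient was assessed, so that the data for adjustment already exist. The documents do not support that. The sentence on co-morbidity comes before the one introducing the matched controls and may describe only the contouring cohort. If so, the proposed model could not be fitted without further data.

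**Conclusion.** The omission is clear from the text: co-morbidity is assessed, is not a matching factor and is not a covariate, in a comparison with no randomisation described. The consequence is conditional. Bias arises only if co-morbidity differs between the groups and affects the outcome. Under the assumed prevalences and effects, the spurious difference is 0.04 to 0.30 SD and the false-positive rate about 5% to 19%. These figures take no credit for balance achieved through matching, so the true size may be smaller.

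Three stronger readings are not supported:

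- That a co-morbidity difference is in fact being reported as a contouring effect. The documents give no rates from which to say so.
- That weight and all three markers would be biased together and appear to confirm one another. Nothing in the documents establishes that co-morbidity moves them in concert here.
- That adding a co-morbidity covariate would abolish the bias. That holds only when the covariate is the condition responsible.

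The change should be made because it is cheap and protects the main comparison, not because a bias has been shown.

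**What to change.** 1. Name the co-morbidities and confirm that they are recorded in both groups. If controls lack them, obtain them from existing records or state the limitation.
2. For the 3- and 6-month outcomes, make the main analysis a linear model with group, the outcome's pre-surgery value and one prespecified co-morbidity covariate chosen for its relevance to the outcomes. For controls, who have no surgery, define the corresponding baseline visit.
3. Account for the matching, either through the matching factors or through a pair term.
4. Report co-morbidity balance as standardised differences, and do not take a non-significant chi-square or Fisher result as proof of balance.
5. Keep the unpaired t-test as an unadjusted secondary result.
6. If results have already been seen, label the adjusted model a sensitivity analysis.

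**Cost.** A few sentences of analysis wording and a standard SPSS model. If both groups were assessed, no new data are needed. Error degrees of freedom fall from 58 for the t-test to 60 − 4 = 56 with group, baseline and co-morbidity, or 60 − 8 = 52 if age, gender, BMI and length of follow-up enter as single terms. With 60 patients the covariate list should stay this short. The remaining limitation is that a count or any-against-none summary may leave much of the confounding in place, so a specific, outcome-relevant condition is preferable where one can be justified in advance.

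### The stability rule leaves room for weight drift, and drift that differs between the groups would bias the weight comparison because the plan neither matches nor adjusts for it

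*Combined protocol and SAP*

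**What the plan says.** All references are to the combined protocol and SAP.

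- **Stability rule.** Under Patients and methods it governs the timing of surgery: "Body Contouring Surgery will performed when the patient's weight has been stable within 5 kg for at least 3 months". Under Inclusion criteria it appears in general terms: "Post-bariatric patients has been stable within 5 kg for 3 months". Neither place says whether 5 kg is a total range or a margin either side, and neither mentions direction or slope. No minimum time since the sleeve is listed.
- **Who the criteria cover.** The first inclusion criterion is "Post-bariatric (sleeve) patients will do body contouring surgery". Read literally, no control can meet it.
- **Groups.** "Group (A): 30 patients will do Post-bariatric body contouring procedure"; "Group (B): 30 patients as a control group will not do body contouring surgery". No randomisation is described.
- **Matching.** "Matching will be based on age, gender, BMI at the time of bariatric surgery, type of bariatric surgery procedure, and length of follow-up".
- **Outcome.** Weight is recorded preoperatively and at months 3 and 6. The Evaluation section describes "Documentation of the patient weight and BMI after post-bariatric body contouring surgery for 6 months". Excised tissue is subtracted from net weight loss. No date is given from which a control's 3 and 6 months are counted.
- **Analysis.** Statistical analysis names an unpaired t-test between the two groups for quantitative variables, two-sided at 0.05. It names no covariates and does not say whether weight is tested as a change or as an absolute value.

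**The concern.** Weight after a sleeve can still be moving when a patient enters. The rule bounds that movement over 3 months, and the outcome then runs for 6 months, twice as long. A single preoperative weight gives the level at entry but not the slope, so two patients of equal baseline weight may be heading in opposite directions.

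This matters if the groups differ in average slope at entry. Group A is certainly selected at a qualifying plateau, because surgery is timed to it. Controls have no operation to time, and it is not clear that they must satisfy the same rule. If controls are regaining while Group A is flat, contouring will appear to help. If controls are still losing, a real benefit could be hidden. Body weight is named in the study title, so this comparison is central.

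**Working it through.** **Inputs from the plan:** 30 per group; 5 kg over 3 months; 6-month outcome; two-sided 0.05. The plan gives no effect size, SD or power, so there is no figure of its own to reproduce. The SDs and drift distributions below are assumptions, and the t-test is taken to be on 6-month change.

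**1. Permitted drift for one patient.** 5 kg / 3 months = 1.67 kg per month. Over 6 months that is 10 kg if it continues unchanged, or 5 kg if it halves. If the rule means 5 kg either side (a 10 kg range), the ceiling is 20 kg. These are limits for an individual, not expected values.

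**2. Drift common to both groups.** In 20,000 simulated trials, with a residual SD of 3 kg and drift carried forward linearly, both groups lost between 0 and 5 kg per 3 months (uniform). The between-group difference was 0.0 kg and the false-positive rate 5.1%, although Group A alone changed by -5.0 kg. The control group removes shared drift.

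**3. Drift that differs between groups.** With no contouring effect and a difference D in mean 6-month drift, SE = SD × √(2/30) and

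P(reject) = Φ(D/SE - 1.96) + Φ(-D/SE - 1.96).

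For D = 2 kg:
- SD 5 kg: SE = 5 × 0.258 = 1.29; D/SE = 1.55; P = 0.34.
- SD 8 kg: SE = 8 × 0.258 = 2.07; D/SE = 0.97; P = 0.16.

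| D over 6 months | SD 5 kg | SD 8 kg |
|---|---|---|
| 0 kg | 5% | 5% |
| 1 kg | 12% | 8% |
| 2 kg | 34% | 16% |
| 3 kg | 64% | 31% |

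**4. Comparison with what the study can detect.** At 80% power the detectable difference is (1.96 + 0.84) × √(2/30) = 0.72 SD, which is 3.6 kg at SD 5 kg and 5.8 kg at SD 8 kg. A differential drift of 2 to 3 kg is therefore a large fraction of the smallest effect the trial could reliably find.

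**5. Chance imbalance.** If 3-month drift is uniform from -5 to +5 kg in both groups, its SD is 10/√12 = 2.89 kg. The SE of the group difference is 2.89 × √(2/30) = 0.745 kg, so the 95% range is ±1.46 kg per 3 months, or ±2.9 kg over 6 months if drift continues. The simulated false-positive rate in this case stays at 5.1%, because the extra spread is already in the t-test's standard error. The cost is precision: the SD of 6-month change rises from 3 to 6.5 kg, and the detectable difference from 0.72 × 3 = 2.2 kg to 0.72 × 6.5 = 4.7 kg.

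**The case against.** The strongest defence is that the plan already has several protections. It has a concurrent 1:1 control group, matching that includes length of follow-up, a BMR-based diet worded for all patients, and a between-group test with no before-after test in Group A. The stability criterion is also listed for post-bariatric patients generally, so controls may well be under it. A 5 kg movement may be fluctuation rather than trend, and nothing in the documents shows that a slope at entry persists.

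Much of this stands. A reader might infer that the stability window is the only safeguard and that all pre-existing drift is credited to contouring. The documents do not support that: shared drift cancels (step 2). Nor should the ±2.9 kg in step 5 be read as bias.

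The defence does not dispose of differential drift. Length of follow-up, even if counted from the sleeve, is only a partial proxy for current slope. The matched BMI is that at bariatric surgery, not at entry. The general wording of the stability criterion sits beside a first criterion that only Group A can meet, so the documents do not settle whether controls are covered. Without an index date, a control's qualifying 3-month window is undefined even if the rule does apply.

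**Conclusion.** The concern holds for drift that differs between the groups. The rule allows residual movement of up to 5 kg in 3 months in either direction. Non-random allocation, matching that omits current weight and recent trajectory, unclear control eligibility, no control index date and an unadjusted t-test together mean that a group difference in drift would be read as an effect of contouring.

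A 2 kg difference over 6 months would give a false-positive rate of about 34% to 16% for an assumed SD of 5 to 8 kg. The calculation also assumes a t-test on change and no true effect. Whether such a difference exists, and in which direction, cannot be judged from the documents. The 10 kg figure is an individual ceiling and should not be taken as an expected group difference. This should be corrected, but it does not invalidate the design.

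**What to change.** Leave the stability threshold unchanged. Then:

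1. State that the stability criterion applies to both groups, reword the first inclusion criterion so that controls can meet the list, and say which reading of 5 kg was applied.
2. Give each control an index date, for example the matched patient's surgery date, and count baseline, 3 and 6 months from it.
3. Take the dated weights at the start of the 3-month window and at entry from the eligibility records of both groups.
4. Replace the unadjusted t-test for weight with an ANCOVA of 6-month weight change, net of excised tissue, on group, baseline weight, pre-entry 3-month change and months since sleeve.
5. Report the mean pre-entry change by group.

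The cost is small. Three covariates reduce the residual degrees of freedom from 58 to 55 with 60 patients, and no visits or patients are added. Applying the rule requires the pre-entry weights, but the plan schedules no weight before the preoperative one, so some retrieval is likely, mainly for controls. A change computed from two weights is a noisy measure of slope, so adjustment will remove part of the bias rather than all of it. If control pre-entry weights cannot be found, the report should say so and limit its conclusion on weight accordingly.

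### Net weight loss is corrected for excised tissue, but no matching rule is stated for BMI, so Group A's BMI change may include the resected mass

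*Combined protocol and SAP*

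**What the plan says.** In Patients and methods, just before the inclusion criteria, the plan states its only correction for resected tissue: "The weight of excised skin and fat in contouring surgery will be documented and removed from the net weight loss". The same section confirms that the quantity will be available: "Weight of the resected tissue will be recorded".

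BMI is paired with weight throughout. Item 1 under Evaluation of the patients reads "Documentation of the patient weight and BMI after post-bariatric body contouring surgery for 6 months". The schedule in Patients and methods reads "Weight and BMI documentation will occur after body contouring surgery before body contouring surgery and 3 and 6 months after". No sentence defines the weight from which BMI is calculated, and none names the reference reading for change.

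Only one group loses tissue: "Group (A): 30 patients will do Post-bariatric body contouring procedure", while "Group (B): 30 patients as a control group will not do body contouring surgery". Under Statistical analysis, quantitative variables are "compared between the two groups utilizing unpaired Student's t- test", two-tailed at 0.05. That sentence is general, so it covers BMI. It does not say whether change or the follow-up value is compared.

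**The concern.** The plan recognises that tissue removed by the surgeon is not weight lost by the patient, and corrects weight loss for it. BMI has the same weight in its numerator, so the same tissue enters BMI unless it is corrected too. Because Group B has no resection, any uncorrected tissue falls on Group A alone and always lowers its BMI.

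The study asks whether contouring affects body weight and metabolism. If BMI is calculated in the ordinary way, from measured weight, the group comparison can reach significance with no physiological effect. It can also disagree with the corrected weight result, and the plan has no rule for which to believe.

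The schedule sentence adds a second uncertainty. Read literally, it lists a reading after surgery as well as one before, and does not say which is the baseline. The choice decides which of the two outcomes is affected.

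**Working it through.** **Inputs from the documents.** 30 patients per group; unpaired t-test; two-sided 0.05; resected tissue in Group A only. The plan gives no BMI shift, power or effect size, so there is no stated figure to reproduce.

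**Inputs assumed.** Resected mass R of 1 to 5 kg; height h of 1.65 m (range 1.55 to 1.75 m); SD of BMI change of 1, 2 or 3 kg/m²; SD of follow-up BMI of 4, 5 or 6 kg/m². R and h are taken as the same for every Group A patient.

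**Step 1: tissue in the BMI change.** Let W0 be pre-operative weight, Wt the weight at 3 or 6 months, and T the loss apart from tissue (negative for regain). Then Wt = W0 − R − T, and

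measured BMI change = (Wt − W0)/h² = −(R + T)/h².

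The tissue part is R/h². In Group B, R = 0. With h² = 1.65² = 2.7225, R of 1, 2, 3 and 5 kg gives 0.37, 0.73, 1.10 and 1.84 kg/m². Across heights of 1.55 to 1.75 m, 1 kg gives 0.42 to 0.33, 3 kg gives 1.25 to 0.98, and 5 kg gives 2.08 to 1.63.

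Tissue is one component of the change. With R = 3 kg, a further true loss of 2 kg gives −5/2.7225 = −1.84 kg/m², of which 1.10 is tissue; a true regain of 2 kg gives −1/2.7225 = −0.37.

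**Step 2: rejection rate with no true effect.** Noncentrality = (R/h²)/(SD × √(2/30)), with √(2/30) = 0.258 and 58 degrees of freedom. For R = 3 kg and SD 2: 1.10/(2 × 0.258) = 2.13, giving 56%. Chance of p ≤ 0.05, in percent, at 1.65 m:

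| R (kg) | Shift (kg/m²) | Change, SD 1 | Change, SD 2 | Change, SD 3 | Follow-up, SD 4 | Follow-up, SD 5 | Follow-up, SD 6 |
|---|---|---|---|---|---|---|---|
| 1 | 0.37 | 29 | 11 | 7.5 | 6.4 | 5.9 | 5.6 |
| 2 | 0.73 | 80 | 29 | 15 | 11 | 8.7 | 7.5 |
| 3 | 1.10 | 99 | 56 | 29 | 18 | 13 | 11 |
| 5 | 1.84 | ~100 | 94 | 64.5 | 42 | 29 | 21 |

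With R added back before BMI is computed, the shift is 0 and the rate returns to 5%.

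**Step 3: the baseline.** The net loss wanted is T = W0 − Wt − R.

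- Pre-operative reference: the written rule gives W0 − Wt − R = T, which is right. Measured BMI change carries R/h².
- Immediate post-operative reference, W0 − R: measured BMI change is −T/h², free of tissue. The written rule, however, gives (W0 − R) − Wt − R = T − R. The tissue is subtracted twice, and Group A's net loss is understated by R.

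For change from one common baseline the two errors therefore cannot occur together, but neither baseline makes both outcomes right if BMI is left as measured.

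**The case against.** The strongest reply is that the plan is silent on BMI and does not say it is left uncorrected. BMI is a function of weight, and an analyst who had already corrected the weight could compute BMI from it. That stands: a reader might infer a decision to correct one outcome and not the other, and the text does not show one. It does not close the gap, because BMI normally means measured weight over height squared and nothing in the plan directs otherwise.

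A reader might also infer that the whole BMI fall in Group A would be tissue. Step 1 shows this is true only if weight does not otherwise change.

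A third tempting reading is that net weight loss will be subtracted twice. That rests on a garbled sentence. The parallel sentence for the inflammatory and cardiac markers lists one pre-operative reading followed by 3 and 6 months, so a pre-operative baseline is the natural reading, and under it the weight rule is correct. The documents support asking for the baseline to be named, and no more than that.

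On size, mass, height and SD are all assumed, and the effect is small in places: a 1 kg resection with a change SD of 3 gives 7.5%. The listed procedures include some, such as facelift, where little tissue may be removed. Finally, no primary outcome is named, and the list of post-procedure data mentions weight changes but not BMI. BMI is nevertheless half of the first evaluation item.

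**Conclusion.** The concern holds in conditional form. The plan corrects net weight loss for excised tissue and states no matching rule for BMI. If BMI is calculated from measured weight, Group A's change from the pre-operative value includes R/h² and Group B's does not. That is a one-sided bias towards surgery, so more is at stake than a missing detail.

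The size depends on facts the documents do not give. At 1.65 m and a change SD of 2, the false-positive rate runs from about 11% at 1 kg to 94% at 5 kg, against a nominal 5%. If follow-up values are tested with SD 5, it is about 13% at 3 kg and 29% at 5 kg. These figures illustrate the range and do not predict this trial's result. The documents do not establish that BMI will go uncorrected, that the fall will be tissue alone, or that tissue will be subtracted twice.

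**What to change.** Apply one rule to both outcomes:

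- For each Group A patient at 3 and 6 months, adjusted weight = measured weight + recorded resected weight, and adjusted BMI = adjusted weight/height². In Group B the adjusted and measured values are the same.
- Rewrite the schedule sentence so that the pre-operative reading is the reference. Net loss = pre-operative weight − visit weight − resected weight.
- Compare the groups on adjusted weight and adjusted BMI, and state whether change or the follow-up value is tested.
- Show measured BMI alongside, labelled as including tissue removal.
- Where liposuction or implants are used, add the aspirate weight and deduct the implant weight if these were recorded. The plan does not say that they are.

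Resected weight is already to be recorded, and height is already needed for BMI and the metabolic-rate formula, so the core change needs no new data. The cost is two derived variables, one paragraph of text, and a BMI result less favourable to surgery.

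### The unpaired t-test makes no stated use of the pre-surgery values, so in this non-randomised comparison existing group differences can enter the estimated effect

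*Combined protocol and SAP*

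**What the plan says.** **Design (Patients and methods).** There are 60 patients in two groups of 30, and no randomisation is mentioned. The groups differ by whether contouring is done: "Group (A): 30 patients will do Post-bariatric body contouring procedure", and "Group (B): 30 patients as a control group will not do body contouring surgery". On the control match: "Matching will be based on age, gender, BMI at the time of bariatric surgery, type of bariatric surgery procedure, and length of follow-up".

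**Measurements (Patients and methods; Evaluation of the patients).** Weight and BMI: "Weight and BMI documentation will occur after body contouring surgery before body contouring surgery and 3 and 6 months after". The wording is garbled, but it is most naturally read as before surgery, 3 months and 6 months. The three markers follow that schedule: "hsCRP and BNP before the body contouring surgery and 3 and 6 months after". The laboratory tests have one follow-up: "Routine investigations (CBC, UR & CR, Lipid profile and RBS) will be done before body contouring surgery and 6 months after".

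**Analysis (Statistical analysis).** "Quantitative variables were presented as mean and standard deviation (SD) and compared between the two groups utilizing unpaired" Student's t-test, two-sided at 0.05. No covariate, change score, repeated-measures model or matched analysis is named.

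**Hints of a change score.** There are two, both for weight only. Weight changes are listed under Post-procedure data, and the excised tissue is to be deducted from net weight loss. BMI, the markers and the laboratory tests have no change definition.

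**The concern.** An unpaired t-test on follow-up values estimates the contouring effect only if the groups would otherwise have had the same mean at that visit. Nothing in the design secures this. Two patients with equal BMI at bariatric surgery may have lost very different amounts by the time one has contouring. Weight and the inflammatory and cardiac markers at study entry are not matching variables. One matching variable, type of bariatric procedure, does no work, because the exclusion criteria admit sleeve patients only. The requirement of weight stable within 5 kg limits drift within a patient; it does not bring the two groups to the same level.

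Two things are at stake. The first is bias: a gap present before surgery is reported as an effect of surgery. The second is precision: if values are stable within a patient, ignoring the baseline leaves avoidable between-patient variation in the comparison. Both bear on body weight and metabolism, the outcomes in the study's title.

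**Working it through.** **Inputs.** From the documents: 30 per group, two-sided 0.05, unpaired t-test (58 df). The documents give no sample-size calculation, SD, target effect or baseline-to-follow-up correlation, so there is no planned figure to reproduce beyond 30 + 30 = 60. Assumed: baseline gap 0.2 to 0.5 SD, correlation r from 0.5 to 0.9, weight SD 14 kg, 80% power.

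**Step 1. False positives on raw follow-up values, gap persisting, no true effect.** The noncentrality is gap / √(2/30) = gap / 0.258, and the critical value is t(0.975, 58) = 2.00.

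- Gap 0.2 SD: 0.2 / 0.258 = 0.77, false positives 12%.
- Gap 0.3 SD: 0.3 / 0.258 = 1.16, false positives 21%.
- Gap 0.5 SD: 0.5 / 0.258 = 1.94, false positives 48%.

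For scale, two independent random samples of 30 would differ by chance with a standard error of 0.26 SD.

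**Step 2. Three analyses compared.** Simulated false-positive rates (20,000 runs per setting, no true effect, range over r = 0.5, 0.7, 0.9):

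| Gap and its behaviour | Raw follow-up | Change score | Baseline-adjusted |
|---|---|---|---|
| 0.3 SD, persists | about 21% | about 5% | 6–10% |
| 0.5 SD, persists | about 48% | about 5% | 7–18% |
| 0.3 SD, regresses to the mean | 9–18% | 6–9% | about 5% |
| 0.5 SD, regresses to the mean | 16–40% | 7–16% | about 5% |

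If the gap persists, adjustment leaves bias: for a 0.5 SD gap, 0.05 SD at r = 0.9 and 0.25 SD at r = 0.5. If the gap regresses, the change score is biased in the opposite direction by the same amounts. Adjustment does better than the raw test in every row. The change score does too, except that at r = 0.5 with a regressing gap it is no better.

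**Step 3. Precision for weight.** With 30 per group, the standardised difference detectable at 80% power is 0.736. Multiply by the relevant SD:

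- Raw: 0.736 × 14 = 10.3 kg.
- Change score, SD × √(2(1 − r)): at r = 0.9, 0.736 × 14 × √0.20 = 4.6 kg; at r = 0.8, 0.736 × 14 × √0.40 = 6.5 kg.
- Adjusted, SD × √(1 − r²): at r = 0.9, 0.736 × 14 × √0.19 = 4.5 kg; at r = 0.8, 0.736 × 14 × √0.36 = 6.2 kg.

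The variance ratio of adjusted to change score is (1 − r²) / (2(1 − r)) = (1 + r)/2, that is 0.95 at r = 0.9 and 0.90 at r = 0.8.

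**Step 4. Precision for markers.** The residual variance after adjustment is 1 − r² of the raw variance: 0.75 at r = 0.5 (a 25% cut) and 0.51 at r = 0.7 (a 49% cut). A change score gives 2(1 − r): 1.00 at r = 0.5 (no gain) and 0.60 at r = 0.7.

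**The case against.** The best reply is that an unpaired t-test can be run on changes, and that the plan twice describes weight as a change. A reader might infer from the statistical section that raw 6-month weights will be compared, and that adjustment would bring the detectable difference from 10.3 kg down to 4.5 kg. The documents do not support that inference, because they do not say which quantity is tested. If weight is analysed as change, adjustment gains only 0.1 kg at r = 0.9 and 0.3 kg at r = 0.8. This part of the objection stands. For weight, the defect is that the analysed quantity is unspecified. It does not extend to BMI, the markers or the laboratory tests, for which no change is mentioned.

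The matching should also narrow any gap, and the chance figure of 0.26 SD ignores it. That is fair, but the matching does not act on study-entry values, and the planned test ignores the pairs.

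A reader might further infer that the groups are self-selected. The documents say that patients are divided into two groups with a matched control group; they do not say how controls were chosen. What can be said is that allocation is not described as random.

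Finally, adjustment is not clearly superior to a change score here. Weight stability before surgery makes a persistent weight gap plausible, and that case favours the change score. The documents do not settle whether a gap would persist or regress, so both results are needed.

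**Conclusion.** The concern holds. The plan schedules baseline values and states no use of them in its only between-group method, in a comparison that neither randomisation nor the matching protects at study entry. It is clearest for BMI, the markers and the laboratory tests; for weight, the fault is an undefined analysis variable.

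If follow-up values are tested and a gap of 0.3 to 0.5 SD persists, the false-positive rate is about 21% to 48% instead of 5%. If the gap regresses to the mean, it is 9% to 40% over r = 0.5 to 0.9. The precision loss is large only against the raw-value reading. All gaps, correlations and the 14 kg SD are assumptions; the direction of the precision result holds for any positive r. The figures show what the plan leaves open, not that a gap of this size exists.

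**What to change.** 1. For each outcome with a baseline value, replace the t-test by a baseline-adjusted model of change from baseline. For weight, BMI, TNF-alpha, hsCRP and BNP, use a mixed model with group, visit, group-by-visit and the baseline of that outcome. For laboratory tests with one follow-up, use ANCOVA.
2. Include the matched pair, or the matching variables, in the model.
3. Define the Group B baseline. Every baseline is placed before a surgery that Group B does not have. Use the value at an index date corresponding to the matched case's pre-surgery visit.
4. State the definition of weight change in the statistical section, including the deduction of excised tissue that the plan already intends.
5. Report the adjusted group difference at 6 months with its 95% CI, and the change-score difference alongside it. If the two disagree, say so: adjustment is biased when a gap is stable, and the change score when it regresses.

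The cost is SAP wording and a little more analysis work. No new measurements are needed provided that controls were measured at a date that can serve as their baseline, which the documents do not establish. Adjustment reduces confounding by baseline values but does not guarantee its removal, and the report should say so.
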